1.0 OVERVIEW

Nephrotic syndrome is the most common acquired kidney disease in children.¹ Affected children have recurrent episodes (or relapses) of proteinuria that may lead to life-threatening complications including sepsis, peritonitis and thromboembolism.² The goals of treatment are to induce remission of proteinuria, reduce the number of relapses, minimize toxicity of treatments and delay kidney damage.³ The first-line treatment for nephrotic syndrome is oral steroids, and many children will need repeated courses of steroids for relapsing disease.^{2,4} However, steroid treatment is associated with many side effects, including obesity, growth retardation, hypertension, cataracts, poor bone health, and cosmetic effects.^{2,5-15} Various other non-steroid immunosuppressive drugs are often used in the course of illness to decrease frequency of relapses and to avoid side effects of prolonged and recurrent steroid use.¹⁶ Treatment protocols for relapsing nephrotic syndrome are therefore complex, requiring multiple drugs and multiple courses of therapy over long periods of time for disease control.

International clinical practice guidelines are available to guide treatment of nephrotic syndrome;¹⁷ however, many of the recommendations are based on poor quality evidence and very few randomized controlled trials - leading to considerable debate among physicians regarding best treatment approaches.^{18,19} As a result, drug treatment protocols and processes of care for childhood nephrotic syndrome are highly variable among physicians and care centres; evidence practice gaps also exist.^{20,21} In a survey of Canadian pediatric nephrologists, we found striking variation in dose and duration of steroids and second line agents reportedly used for first presentation and relapses of nephrotic syndrome.²² Lack of consensus between physicians and centres regarding best treatment approach can lead to a frustrating experience for patients and families, poor satisfaction with clinical care, and sub-optimal outcomes.^{19,23} Using a priority setting survey, we identified that addressing these issues in the management of childhood nephrotic syndrome is the top priority for the Canadian pediatric nephrology community.

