2.2 Steroids are the treatment of choice for first presentation and subsequent relapses of nephrotic syndrome. Clinical response to steroids is the most important predictor of disease course.² Steroid sensitive patients typically respond to treatment with remission of proteinuria within 2 weeks of therapy and maintain normal kidney function. Steroid resistant patients, defined as those who fail to achieve complete remission of proteinuria after 8 weeks of steroid therapy, have a high risk (>50% in 5 years) of kidney failure.^{32,33} Approximately 90% of children with nephrotic syndrome are steroid sensitive, and they will be the focus of our study.^{34,35} Among these patients remission is achievable with steroid treatment; however, relapses are common requiring multiple courses of steroids and steroid sparing immunosuppressive drugs - leading to significant side effects drug toxicity. Of the children who relapse, up to 50% will have frequent relapses (≥ 2 relapses within 6 months of first response or ≥ 4 relapses in any 12 month period) or become steroid dependent (2 consecutive relapses during tapering of steroid therapy, or relapse within 14 days of steroid cessation).^{10,30} Steroid toxicity reported in children with nephrotic syndrome includes growth retardation and obesity,^{7,9,13,36} hypertension,^{11,37} posterior sub-

capsular cataracts,^{6,12} decreased bone mineral density,^{14,15} and impaired glucose tolerance.⁸ Minimizing relapse rates and steroid exposure are the most important goals in caring for these patients and remain the most relevant clinical outcomes.

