Patient enrollment: Two team members from each participating site will be primary contacts for the study (one physician and one nurse/research staff). Every 2 weeks these individuals will generate a list of patients seen with nephrotic syndrome by reviewing inpatient and outpatient data (clinic scheduling records) to determine eligibility. All patients with a clinical diagnosis of nephrotic syndrome who meet the inclusion and exclusion criteria will be introduced to the study by the primary treating physician. The site investigator will approach patient/parents to obtain informed consent and will also obtain assent from older patients (age >12 years). Patients will be enrolled in the study if they meet inclusion criteria and

their legal guardian has given informed consent. Consent forms will be available in English and French. Logs of all patients screened and consented, and for those who declined the reason will be kept.

Physician enrollment: Informed consent will be obtained from physicians within participating nephrology care teams to allow their demographic information (age, gender, location of nephrology training, years in practice) to be collected. Physician data will be linked to their patient's data in the nested data architecture. Once linked, physician identifying information will be removed. If a consenting patient's physician declines to participate in the study, the patient's data will be linked to a generic category of 'unknown physician.'

Patient data being collected: Study data will be collected at the following study points (see Figure below and more details shown in Appendix, Figure 2): 1) study entry (whether first presentation, first relapse or second relapse); 2) at the beginning of all subsequent relapses [defined as proteinuria > 3+ on dipstick, > 3g/L on urinalysis or urine protein to creatinine ratio > 200 mg/mmol for 3 consecutive days or start of full dose steroids (60 mg/m² or 2mg/kg)]; 3) at the end of first presentation and end of all subsequent relapses [defined as both remission of proteinuria – negative or <1.0 g/L protein on dipstick for 3 consecutive days, and off steroids]; 4) study visits every 6 months after entry; 5) at start of all steroid sparing agents; 6) at time all kidney biopsies; and 7) study end.

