Outcome: The primary outcome of interest is relapse rate (number of relapses/per person unit time). Relapse rate is the most clinically relevant outcome for nephrotic syndrome and the best indicator of morbidity experienced by patients; this outcome definition is consistent with prior literature in this area.⁴⁰

Exposure: The exposure is steroid prescribed per unit time - that is the total dose patients were prescribed as treatment for episodes of proteinuria divided by the sum of duration of 'days on steroids' during observation period. Days on steroids is defined by the sum of the length in days of all episodes (see definition of episode in section 3.1, also graphically represented in Appendix Figure 4) observed. This definition is consistent with measures of steroid exposure used in prior nephrotic syndrome steroid dosing studies conducted in Europe and in a Canadian study of steroid associated osteoporosis in children.^{38,55} Systemic steroid exposure (both oral and intravenous) will be converted into prednisone equivalents (mg/m^2) using standard dose conversion tables and weight based dosing criteria [mg/kg] will be converted to mg/m^2 .

Analysis plan: The unit of analysis is the patient. Given that the main outcome of interest is relapse rate, we will use Poisson regression models with steroid prescribed per unit time as the exposure and relapse rate per unit time as the outcome, adjusting for patient level variables (age, gender, ethnicity, household income, parental education) and episode at entry into study (either first presentation, first relapse or second relapse), and taking into account time at risk. We are not using multi-level (hierarchical) analysis in this objective, as there is no clustering at the patient-level. There is only one measurement per patient, relapse rate adding all episodes experienced by one patient as a count.

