Feasible sample and power considerations: We estimated a feasible sample based on data gathered from 2 sources: an ongoing longitudinal study of children with nephrotic syndrome (INSIGHT study, led by [name]) recruiting a Toronto based cohort,⁵³ and our preliminary data (Appendix Figure 5 for preliminary recruitment rate). Based on the expected consent rate of 72%, and estimated drop out of 10% (due to loss to follow-up or steroid resistance), we estimate that we will be able to enrol and follow, at least, 520 patients over a period of 4.0 years (65 patients every 6 months). In our preliminary work, we have already enrolled 77 patients from 6 sites, thus our total estimated sample is 597 patients.

Although we hypothesize that increasing steroid dose prescribed per unit time will be associated with decreasing relapse rates, no studies to date have reported a specific magnitude of the effect of steroid prescribed per unit time on relapse rates. A systematic review of available clinical trials examining this issue, published in 2007, only reports on risk ratios based on the dichotomous outcome of any relapse at a pre-specified time interval (usually 12 or 24 months).⁴⁰ Our outcome of interest is an actual rate (count of relapses/person years). Hence, a power based, effect size dependent sample size calculation was not performed. At a significance level $\alpha = 0.05$, and under the following assumptions of a mean daily steroid dose of $30.64 \text{ mg}/\text{m}^2$ with a standard deviation (of the dose) of 8.85, a base rate of relapse of 1.68 per person year, average follow up (time at risk of relapse) of 2 years and a conservative correlation (R^2) of the steroid dose with other covariates of 0.2, we would have 90% power to detect an incidence rate

ratio of 0.989 or smaller (i.e. a larger effect size) in a multiple Poisson regression. We are allowing for a 2 tailed test to allow the possibility of the effect being on either side of the null.

3.3 Work Plan for Objective 2

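### Objective 1 pools follow-up before and after steroid-sparing agents, so its dose–relapse association can be biased if dose per treated day changes after an agent starts or if starting one depends on dose

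*Protocol*

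**What the plan says.** For Objective 1 the protocol (section 3.2, Analysis plan) commits to this: "we will use Poisson regression models with steroid prescribed per unit time as the exposure and relapse rate per unit time as the outcome". The patient is the unit, and all of a child's relapses form a single count. The exposure is total prescribed dose over the observation period divided by days on steroids. The adjusters are age, sex, ethnicity, income, parental education and the episode at which the child entered. Steroid-sparing treatment is not a covariate, a stratum, a censoring event or a point at which follow-up is split.

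Elsewhere the protocol gives these drugs a clear role:

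- Section 1.0 says that non-steroid "immunosuppressive drugs are often used in the course of illness to decrease frequency of relapses", and also to spare children long and repeated steroid treatment.
- Section 2.2 says that, of children who relapse, "up to 50% will have frequent relapses" or become steroid dependent.
- Section 3.1 requires children who enter at a relapse to do so before any such agent; children who enter at first presentation have had no steroids. Use therefore begins during follow-up, which section 3.2 puts at up to 4 years.
- Section 3.1 makes a data collection point "at start of all steroid sparing agents". Under the cohort description in the same section, these data serve only to describe time to agent, choice and indication.

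The limitations (section 4.0) name unknown confounders and adherence, but not these agents.

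**The concern.** A drug given to reduce relapses starts part-way through follow-up, in children selected by their relapse history, and the primary model does not distinguish time before it from time after it. If average dose per treated day also differs between those periods, or between children who do and do not start an agent, the model can attribute to steroid dose what belongs to the agent or to the reasons for starting it. Section 7.0 presents Objective 1 as showing the impact of variable steroid treatment on outcomes, and section 6.0 uses the results to draft best-practice approaches. The effect the study is sized to detect is small per unit of dose, so a modest distortion could mimic it or hide it.

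This is not a detail left to an analysis plan. The protocol itself fixes both the single pooled record and the adjustment set.

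**Working it through.** **1. The plan's own figure.** Inputs from section 3.2: N = 597, two-sided α = 0.05 ("We are allowing for a 2 tailed test"), mean dose 30.64 mg/m², SD 8.85, base rate 1.68 relapses per person-year, 2 years at risk, R² = 0.2. The claim is that "we would have 90% power to detect an incidence rate" "ratio of 0.989 or smaller (i.e. a larger effect size) in a multiple Poisson regression". The dose unit is not stated; 1 mg/m²/day is inferred from the SD.

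Wald form, normal dose, base rate taken at dose zero, b = ln IRR:

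power = Φ(√[N(1−R²) · T · rate · exp(b·mean + b²·SD²/2) · SD² · b²] − 1.96)

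- b = ln 0.989 = −0.01106
- N(1−R²) · T · rate = 597 × 0.8 × 2 × 1.68 = 1604.7
- exp(−0.3389 + 0.0048) = 0.716
- SD² · b² = 78.32 × 0.0001223 = 0.00958
- √(1604.7 × 0.716 × 0.00958) = 3.32; Φ(3.32 − 1.96) = 0.913

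The 90%-power IRR is 0.9893. The stated figure reproduces, so the point concerns interpretation, not arithmetic.

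**2. How many children could be affected.** Sections 2.1 and 2.2 give 70–90% relapsing and up to 50% of those with frequent relapse or dependence: 0.70 × 0.50 = 35% to 0.90 × 0.50 = 45%. This is a ceiling on frequent relapse or dependence, not an estimate of agent use.

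**3. What pooling does.** Settings are assumed: 597 patients, frailty variance 0.6, agents started after repeated relapses (about 33% of patients, 22–23% of person-time afterwards), relapse rate halved on the agent, 60 runs per setting, start not dependent on dose.

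| Change in dose per treated day on agent (mg/m²) | Pooled IRR, true 1.000 | Pooled IRR, true 0.989 |
|---|---|---|
| −8 | 0.994 | 0.985 |
| −4 | 0.997 | 0.988 |
| 0 | 0.999 | 0.991 |
| +4 | 1.004 | 0.994 |
| +8 | 1.007 | 0.997 |

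Splitting or stopping follow-up at the start gave 0.999–1.000 and 0.989–0.990. Simulation error matters at the third decimal: the model-based standard error of b is about 0.01106/3.32 = 0.0033, so for a mean of 60 runs it is at least 0.0033/√60 ≈ 0.0004.

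A second simulation, also on assumed settings, had 43–45% of patients starting an agent. Under a true IRR of 1.000 the pooled IRR ran from 0.984 to 1.014 over the same dose changes, against 0.998–1.002 after cutting or splitting. It showed no bias when dose per treated day was unchanged and start did not depend on dose.

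Relative to the detectable log IRR, the extremes of the second simulation are |ln 0.984|/0.01106 = 1.46 and ln 1.014/0.01106 = 1.26. Those of the first are |ln 0.994|/0.01106 = 0.54 and ln 1.007/0.01106 = 0.63. If the agent cuts the relapse rate to 0.3 instead of 0.5 in the first simulation, the null range narrows to 0.997–1.003.

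**4. When start depends on dose.** With a true IRR of 1.000 in the first simulation:

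- Higher dose, more starts: pooled 0.992–0.994, split or stopped 0.994–0.995.
- Lower dose, more starts: pooled 1.005–1.008, split or stopped 1.004–1.006.

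In the second simulation the pair was 0.9975 pooled and 0.9964 cut. The two analyses can agree and both be wrong.

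**5. Cost in power.** Multiplying T by the share of person-time kept, power at IRR 0.989 is 0.889 with 8% removed, 0.864 with 15%, 0.832 with 22.5% and 0.769 with 34%. The shares are assumed.

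**The case against.** The strongest reply is that no mechanism is shown. A reader might infer that these agents must distort the result because they reduce steroid use. The documents do not support that: the exposure is divided by days on steroids, so fewer courses leave it unchanged, and nowhere does the protocol say that dose per treated day changes on an agent. This stands, and it makes the point conditional.

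A reader might also take the 35–45% as uptake and derive a bias as a firm multiple of the detectable effect. That is not supported either. Uptake, the dose change and the size of the agent's effect on relapse are all absent from the documents.

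A third reply concerns the remedy, and it stands too. Episodes open at full dose (60 mg/m², section 3.1) against a mean of 30.64, so cutting at an agent started mid-episode keeps the full-dose phase and loses the taper. In simulations with no true dose effect, such a cut moved the IRR from 1.023 to 1.052, and in another setting from 1.003 to 1.013. The comparison within each pair, not its level, is what matters here.

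Finally, Objective 1 is worded as an association, and supplementary analyses often sit in an analysis plan. But section 7.0 speaks of impact, and the pooled record and adjusters are fixed in the protocol itself.

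**Conclusion.** The point holds in conditional form. As specified, the pooled model can give a biased dose–relapse association, in either direction, if average dose per day on steroids changes after an agent starts or if starting an agent depends on dose. Where neither is so, the simulations found essentially no bias.

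The size is not known from the documents. Under the assumed settings, with changes of −8 to +8 mg/m²/day, the null pooled IRR lay between about 0.984 and 1.014 at the widest and between 0.994 and 1.007 with fewer starters. Either range is material beside a detectable IRR of 0.989, but these are illustrations, not estimates for this cohort. The primary model need not be replaced; its reading needs a planned check that uses the recorded start dates.

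**What to change.** Beside the all-follow-up model, pre-specify an analysis that splits each patient's relapse count, person-time and steroid dose at the first steroid-sparing agent, with an indicator for time after the start. Alternatively, restrict it to time before the start.

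- Assign each steroid episode whole to the period in which it began, so that a mid-episode start does not separate full dose from taper.
- If both periods are kept, allow for two records per patient in the standard errors. State what is done when a period contains no steroid episode, because dose per treated day is then undefined; the restricted version avoids this for time after the start.
- Do not use a whole-period ever/never covariate: agents start in response to earlier relapses.
- Report both results, with a material difference defined in advance. Present such a difference as evidence that the pooled association is not attributable to steroid dose alone. Do not treat agreement as proof of a dose effect, because both can share a bias when start depends on earlier dose or relapses.

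The cost is one more model on data already collected. The split version keeps all person-time. The restricted version loses some: an assumed 8–34% gives power of about 0.89–0.77 at IRR 0.989. The split point is itself related to relapse, which should be stated with the result.

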For Objective 1, we will evaluate association of steroid dose prescribed with relapse rates, adjusting for patient characteristics. For objective 2, we will use multi-level modeling with patients nested within physicians and physicians nested within health centres, to evaluate the association of patient-, physician- and centre-related factors with variability in steroid treatment dose prescribed. An embedded qualitative study utilizing focus groups of health care providers will enrich the quantitative results by providing an understanding of attitudes, beliefs and local factors driving variation in care at participating centres, while considering provider characteristics (training background, experience) and centre characteristics (use of standardized protocols). Quantitative and qualitative results will be integrated (using a convergent parallel mixed methods design) for interpretation at the end of study, and collectively inform strategies for development and implementation of best practice treatment protocols across centres to improve overall provision of care in this patient population. *See adjacent figure for overview of study.*

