2.8 Expected results and significance: We expect to observe differences in relapse rates based on steroid prescribed (Objective 1) and we expect to find that physician and centre characteristics play an important role in determining variation in treatment protocols (Objective 2). Our KT strategies will utilize the collective information gathered in this study regarding steroid prescribed and relationship to outcomes, and factors determining variation in treatments, to develop best practice approaches for treatment of nephrotic syndrome, and to identify physicians and centres most or least likely to implement these approaches. This project will also provide the unprecedented opportunity for every child with nephrotic syndrome and every physician treating children with nephrotic syndrome to be enrolled into the observational cohort, their data being used to inform development, implementation and iterative refinement of treatment protocols, and provide foundational clinical data to prioritize future clinical trials.

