3.0 METHODS

We have conceptualized our study, evaluating clinical care and outcomes of childhood nephrotic syndrome, based on Donabedian's well known 'structure, process, and outcome' framework for health services evaluation.⁵⁴ Our work plan to achieve objectives 1 and 2 (to evaluate association of steroid dose prescribed with outcomes, and to understand sources of variability in treatments), using both quantitative and qualitative methods and a nested data architecture with patients' data linked to their physicians and physicians' data linked to their centres (see adjacent figure), will broadly address structure, process and outcome elements operating at three levels. First in section 3.1 below, we provide details regarding creation and characterization of the prospective cohort – the means by which we will achieve objectives 1 and 2.

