3.1 Cohort Creation and Characterization

Population and setting: All children who present to pediatric nephrology clinics with a clinical diagnosis of nephrotic syndrome will be eligible for enrollment into the longitudinal cohort. All pediatric nephrology centres in Canada (n=13) are participating in this national study (see attached support letters). All pediatric nephrologists who care for children with nephrotic syndrome in Canada are eligible for enrollment.

Enrollment period: The enrollment period for the prospective cohort will last 4.0 years. The observation period will continue for an additional 6 months after the enrollment period (to ensure minimum 6 months follow-up for all patients by end of study).

Inclusion criteria: A patient is eligible to enter the cohort if he/she meets one of the following 2 criteria. See Appendix, Figure 1 for patient enrollment plan.

- A child with **first presentation** of nephrotic syndrome who meets the following criteria: age 1 to ≤17.5 years; edema present; urinalysis shows proteinuria (> 3+ on dipstick; > 3 g/L on urinalysis or urine protein to creatinine ratio > 200 mg/mmol); serum albumin < 25 g/L; and no prior treatment with steroids.
- A child with an established diagnosis of childhood nephrotic syndrome who presents at the beginning of either a **first or second relapse** (defined as proteinuria > 3+ on dipstick, > 3g/L on urinalysis or urine protein to creatinine ratio > 200 mg/mmol for 3 consecutive days) during enrollment period, prior to start of steroid sparing agents or kidney biopsy.

[figure not shown]
Exclusion criteria: Patients will be excluded if they meet one of the following criteria either at enrollment or during course of study: 1) secondary cause of nephrotic syndrome (e.g. lupus, malignancy); 2) C3 low suggesting high likelihood of secondary cause of nephrotic syndrome. Patients ultimately shown to be steroid resistant will be excluded from the final analysis, but will continue to be followed in the prospective cohort. Enrolled patients who turn 18 years of age during the study will exit the study. Further follow-up will be sought for these adult patients using a revised ethics application.

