Outcomes: The primary outcome is steroid prescribed per episode. We will examine: a) total dose patients receive for an episode; and b) average daily dose by dividing the total dose by duration (in days) of the episode. Dose will always be in mg/m² prednisone equivalents. This outcome definition is consistent with measures of steroid exposure used in prior nephrotic syndrome steroid dosing studies.^{38,55} We are evaluating steroid prescription per episode because in this objective, we will study determinants of variability in steroid prescription for episodes of proteinuria rather than patient outcomes related to cumulative exposure of steroids (e.g. relapse rate). All episodes will be categorized either as first presentation or relapse. The secondary outcome will be length of episode in days.

Exposures: Exposure variables of interest are categorized into centre-, physician- and patient-level variables. Centre-level variable is defined as existence of a standardized protocol within centre for treating first presentation and relapses (information will be obtained from the site investigator as existence of centre based protocols [yes/no]). Physician-level variables are gender, year of graduation from nephrology fellowship, and location of nephrology training (Canada vs. outside Canada). These centre- and physician-level variables were shown to impact variability in practice patterns according to our published survey.²² Patient-level variables are age, gender, ethnicity, and status at entry into study (first presentation, relapse). These variables are further described in Appendix, Table 5.

Analysis plan: We will describe the primary and secondary outcomes according to each of centre-, physician- and patient-level characteristics with 95% confidence intervals. To study the associations of centre-, physician-, patient-level characteristics with the primary outcome (steroid prescribed per episode), we will use mixed effects models with fixed effects for centre (standardized protocols yes/no), physician (gender, years in practice, location of training), and patient (age, gender, ethnicity) characteristics and random effects to account for physicians clustering within centre, patients clustering

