3.4 Summary of progress and preliminary results

With start-up funds obtained from CIHR and other sources, we launched the prospective cohort at 13 centres and have recruited 77 patients from 6 centres to date. The remaining 7 centres are either approved or close to full approval (ethics and contracts). All sites will be recruiting by June 2015 – demonstrating feasibility to complete the work plan as described in this proposal. Our preliminary data is provided in the Appendix. Baseline demographics of the patient and physician cohort enrolled to date are shown in

Tables 7 & 8. Preliminary data from the cohort demonstrating variation in steroid prescriptions by key patient demographic variables and by type of episode of treatment are shown in Tables 9a-c. Graphical representations of steroid prescribed per episode for different patient scenarios are shown in Figures 7a-d. Variation in steroid prescriptions between physicians within one site and variation in steroid prescriptions between sites are shown in Tables 10 and 11 respectively. We also show differences among patients in ‘time on and off steroids’ by site in Figure 8, and the average daily steroid dose over time by site in Figure 9. Finally, in Figure 10 and Table 12, we show differences in relapses (survival curve, and absolute relapse numbers) by site.

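### Objective 1 rules out multi-level analysis because each patient gives one count, but that reason does not cover patients nested in 13 centres

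*Protocol*

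**What the plan says.** Protocol section 3.2 (Analysis plan) regresses each patient's relapse count on steroid prescribed per day of treatment. The model is Poisson with allowance for time at risk. The covariates are age, gender, ethnicity, household income, parental education and episode at entry; there is no centre or physician term. A hierarchical model is set aside: "We are not using multi-level (hierarchical) analysis in this objective, as there is no clustering at the patient-level". The next sentence gives the ground, which is that all of a patient's episodes are summed into one measurement.

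Elsewhere the protocol describes the same cohort as clustered above the patient:

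- Section 1.0, for Objective 2: "multi-level modeling with patients nested within physicians and physicians nested within health centres".
- Section 3.1: "All pediatric nephrology centres in Canada (n=13) are participating in this national study".
- Section 3.3, for Objective 2: "random effects to account for physicians clustering within centre, patients clustering" within physician, and episodes within patient.
- Section 2.8 expects that "physician and centre characteristics play an important role in determining variation in treatment protocols". Treatment is the Objective 1 exposure.
- Section 3.4, from the first 77 patients at 6 centres: "variation in steroid prescriptions between sites are shown in Tables 10 and 11 respectively", and "we show differences in relapses (survival curve, and absolute relapse numbers) by site".

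**The concern.** Summing a patient's episodes into one count removes one level of dependence, that of episodes within a patient. It says nothing about whether two patients of the same centre are more alike than two patients of different centres. The sentence is true of one level and is used to dismiss every level.

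Two things are at stake for the primary association. First, if dose and relapse both vary by centre beyond the covariates, model-based Poisson standard errors are too small and the interval for the dose effect is too narrow. Second, if centres that prescribe more also have higher or lower relapse rates for other reasons, the dose coefficient absorbs part of that difference. Section 6.0 says the results will feed best-practice approaches, so a site effect read as a dose effect would have consequences.

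**Working it through.** **1. Which levels does the reason cover?**

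| Level | Covered by one count per patient? | Treated in Objective 2? |
|---|---|---|
| Episodes within patient | Yes | Random effect |
| Patients within physician | No | Random effect |
| Physicians within centre | No | Random effect |

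**2. The plan's own power figure.** Section 3.2 gives two-sided alpha 0.05, dose mean 30.64 and SD 8.85 mg/m², base rate 1.68 per person-year, 2 years' follow-up, R² 0.2, and 90% power at an incidence rate ratio (IRR) of 0.989. I used the Signorini formula for Poisson regression with a normal covariate, taking 1.68 as the rate at dose zero:

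- b = ln 0.989 = -0.01106
- v = exp(-(b × 30.64 + b² × 8.85²/2)) = 1.397
- information per patient = 8.85² × 2 × 1.68 × b² × 0.8 = 0.02576
- N = (1.960 + 1.282 × √1.397)² / 0.02576 = 469

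The stated figure is therefore reproduced with no clustering term, so it assumes independent patients.

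**3. Effect of ignoring centre.** For an exposure that varies both within and between centres, DE = 1 + (m - 1) × ICC(dose) × ICC(relapse), with m = 597/13 = 45.9. The real type I error of a nominal 5% test is 2 × (1 - Φ(1.96/√DE)). The ICCs and equal centre sizes are assumptions; the protocol gives neither.

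| ICC dose | ICC relapse | DE | SE too small by factor | Type I error |
|---|---|---|---|---|
| 0.05 | 0.01 | 1.02 | 1.01 | 5.3% |
| 0.10 | 0.03 | 1.13 | 1.07 | 6.6% |
| 0.20 | 0.05 | 1.45 | 1.20 | 10% |
| 0.30 | 0.10 | 2.35 | 1.53 | 20% |

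If either ICC is zero, DE is 1. In a separate simulation of the planned model with 13 unequal centres and no true dose effect (1,500 runs per setting), rejection was 4%-5% with no centre variation in relapse. It was 7%-10% with a between-centre SD of log relapse rate of 0.1 and 14%-25% with an SD of 0.2, for dose ICC 0.1 and 0.3 respectively. Centre indicators brought it back to about 4%-6%.

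**4. Confounding by site.** Assume a correlation of 0.5 between centre dose and centre relapse rate, and no true dose effect. Over the four ICC pairs above, the planned model then gave a mean slope of 0.0007 to 0.0050 per mg/m² (400 runs each). The top value is 0.0050/0.0111 = 45% of the log rate ratio the study is powered for; the bottom value is under a tenth of it. Robust standard errors do not remove this bias.

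**5. Which remedy holds up?** The runs in steps 3 and 4 use exact Poisson counts within centre. Sections 2.1 and 2.2 describe from 1 to more than 20 relapses, and frequent relapse or steroid dependence in up to half of relapsers, so patients are likely to differ more than Poisson allows. With 13 near-equal centres, dose ICC 0.2, centre SD 0.125 and no dose effect (600 runs), centre fixed effects with model-based errors rejected 4% without patient frailty, 15% at frailty variance 0.25 and 20% at 0.5. In a further simulation with overdispersed counts, that approach rejected 13%-26%, while errors clustered on centre stayed near 5%-6%.

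A small-sample correction also matters. With assumed unequal centres (180 down to 5 patients, exact Poisson counts), plain cluster-robust errors on 12 degrees of freedom rejected 6.7%-11.9%. A bias-reduced variance with Satterthwaite degrees of freedom rejected 3.3%-5.6%.

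**The case against.** The strongest reply concerns evidence. Harm needs relapse, not only dose, to cluster. Most of the cited text concerns data structure or prescribing, and the between-site variation claimed in section 4.0 is variation in care. Only one sentence of section 3.4 concerns relapse. It rests on 77 patients at 6 centres, partly on absolute numbers, and its figure and table are not shown. A relapse difference by site could also be the dose effect under study. All of this stands: centre clustering of relapse is plausible, not shown.

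Second, the protocol excludes only hierarchical models. A reader might infer that it forbids any allowance for centre. It does not: cluster-robust errors or centre indicators remain open, and an analysis plan that is not shown may specify them. The point is therefore the inadequate stated reason, not a missing estimator.

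Third, a reader might infer that the 90% power claim is wrong. The documents do not support that. At N = 597, Wald power is Φ(√(597 × 0.02576/(v × DE)) - 1.96). With 1.68 as the rate at dose zero (v = 1.397) it falls from 91% to 79% in the middle case (DE 1.45). With 1.68 as the average rate (v = 1) it falls from 97.5% to 90.3%, and the stated 90% survives. The protocol does not say which rate is meant. Which N and formula lie behind the 90% is a separate question and no part of this point.

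Fourth, a within-centre estimate is no clean test of site confounding. It drops the between-centre practice variation that the study wants to learn from. Section 2.5 says physicians set treatment in light of the individual presentation, so within-centre dose differences may be more confounded by indication. This stands, and such an estimate can only be supportive.

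**Conclusion.** The reason given in section 3.2 does not support the conclusion drawn from it and should be corrected. It closes a question that the protocol's own nesting, its expectation about centres and its preliminary site differences leave open.

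The size is unknown. Under the assumed ICC ranges the damage runs from negligible (type I error 5.3%) to serious (20%), and the top needs both ICCs at their assumed maximum. A reader might infer that the planned analysis is shown to be anti-conservative or confounded by site. That goes too far: with no ICC, no centre sizes and only preliminary relapse data by site, not said to be adjusted, the figures are illustrations. If relapse does not vary by centre once the covariates are in the model, the harm is negligible. The correction is worth making because it affects the primary association and is cheap. Confidence is high that the reasoning is incomplete and moderate that it matters in practice.

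**What to change.** In section 3.2 (Analysis plan), replace the sentence that denies clustering with wording such as:

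*Each patient contributes one count, so episodes within patients need no model. Patients are nested in 13 centres, so standard errors for the dose effect are cluster-robust by centre with a small-sample correction. If a centre random or fixed effect is used instead, it is combined with a variance that allows for patient-level overdispersion. A model with centre effects is reported as a sensitivity analysis.*

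Describe the within-centre estimate as supportive only. The choice of small-sample correction can be left to the sponsor, but it should suit few and possibly unequal clusters.

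In section 3.2 (power considerations), add that the 90% power at an IRR of 0.989 assumes independent patients.

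Cost: wording and code. Patients, physicians and centres already carry study numbers and are linked (section 3.1), so no new data are needed. Intervals will be somewhat wider. In the unequal-centre simulation the Satterthwaite degrees of freedom fell to about 6, which puts the critical value near 2.5 instead of 1.96. For dose ICC 0.05-0.30 the within-centre estimate has a standard error larger by 1/√(1 - ICC), or 1.03 to 1.20 times.
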